8.1.1 Adverse (Drug) Reaction

All noxious and unintended responses to a medicinal product related to any dose should be considered an adverse drug reaction. “Responses” to a medicinal product means that a causal

relationship between a medicinal product and an AE is at least a reasonable possibility (ie, the relationship cannot be ruled out).

8.1.2 Unexpected Adverse Drug Reaction

An Unexpected Adverse Drug Reaction is defined as an adverse reaction, the nature or severity of which is not consistent with the current Investigator's Brochure.

8.1.3 Assessment of Adverse Events by the Investigator

The Investigator will assess the severity (intensity) of each AE as mild, moderate, or severe, and will also categorize each AE as to its potential relationship to study drug using the categories of yes or no.

Assessment of severity

The severity of all AEs should be graded according to the CTCAE Version 5.0. For those AE terms not listed in the CTCAE, the following grading system should be used:

- CTCAE Grade 1: Mild; asymptomatic or mild symptoms; clinical or diagnostic observations only; intervention not indicated;
- CTCAE Grade 2: Moderate; minimal local or non-invasive intervention indicated; limiting age-appropriate instrumental activities of daily living;
- CTCAE Grade 3: Severe or medically significant but not immediately life-threatening; hospitalization or prolongation of hospitalization indicated; disabling; limiting self-care activities of daily living;
- CTCAE Grade 4: Life threatening consequences; urgent intervention indicated; and
- CTCAE Grade 5: Death related to the AE.

Causality assessment

The relationship of an AE to the administration of the study drug is to be assessed according to the following definitions:

- No (unrelated, not related, unlikely to be related) – The time course between the administration of study drug and the occurrence or worsening of the AE rules out a causal relationship and another cause (concomitant drugs [including alternative, novel treatments for COVID-19], therapies, complications, etc) is suspected; or
- Yes (possibly, probably, or definitely related) – The time course between the administration of study drug and the occurrence or worsening of the AE is consistent with a causal relationship and no other cause (concomitant drugs, therapies, complications, etc) can be identified.

The definition implies a reasonable possibility of a causal relationship between the event and the study drug. This means that there are facts (evidence) or arguments to suggest a causal relationship.

The following factors should also be considered:

- The temporal sequence from study drug administration;

The event should occur after the study drug is given. The length of time from study drug exposure to event should be evaluated in the clinical context of the event.

- Underlying, concomitant, intercurrent diseases;

Each report should be evaluated in the context of the natural history and course of the disease being treated and any other disease the patient may have.

- Concomitant drug;

The other drugs the patient is taking or the treatment the patient receives should be examined to determine whether any of them might be recognized to cause the event in question.

- Known response pattern for this class of study drug;

Clinical and/or preclinical data may indicate whether a particular response is likely to be a class effect.

- Exposure to physical and/or mental stresses; and

The exposure to stress might induce adverse changes in the recipient and provide a logical and better explanation for the event.

- The pharmacology and PK of the study drug.

The known pharmacologic properties (absorption, distribution, metabolism, and excretion) of the study drug should be considered.

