4.3 Stopping Criteria

All AEs should be considered possibly related to study drug unless clearly unrelated or if there is a clear etiology other than study drug such as a pre-existing medical condition, an underlying disease, or a concomitant medication. The decision to have an associated pause in enrollment will be made by the chairperson of the iDMC (with input from the Medical Monitor). The iDMC will oversee the safety and tolerability of FP-025 during the study and determine if it is acceptable to continue, as described in Section 9.2.4. However, safety and tolerability data will be reviewed on an ongoing basis by the Medical Monitor and stopping rules will be applicable starting with dosing of the first patient.

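### The yes/no causality definitions in section 8.1.3 leave a gap: an AE with compatible timing and another identifiable cause fits neither, and the Yes condition conflicts with 8.1.1 and partly with 4.3

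*Combined protocol and SAP*

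**What the plan says.** Section 8.1.3 tells the Investigator to "categorize each AE as to its potential relationship to study drug using the categories of yes or no". There is no third category.

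- **No** applies when the time course between dosing and "occurrence or worsening of the AE rules out a causal relationship and another cause" is suspected. The two conditions are joined by *and*.
- **Yes** applies when the time course "is consistent with a causal relationship and no other cause (concomitant drugs, therapies, complications, etc) can be identified". Again both conditions must hold.

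The same section labels the positive category "Yes (possibly, probably, or definitely related"), and adds: "The definition implies a reasonable possibility of a causal relationship between the event and the study drug".

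Two other sections set a standard for relatedness:

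- Section 8.1.1 treats a response as an adverse drug reaction when a causal relationship "is at least a reasonable possibility (ie, the relationship cannot be ruled out").
- Section 4.3 opens with a default: "All AEs should be considered possibly related to study drug unless clearly unrelated". The sentence then adds a second exemption, for events with a clear cause other than study drug; its examples are pre-existing conditions, underlying disease and concomitant medication.

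**The concern.** The population is severe to critical COVID-19 with ARDS (section 4.1, criterion 4), and all patients receive standard-of-care and/or EUA treatment alongside study drug (section 3.1.1). Section 8.1.3 itself directs the Investigator to look for other drugs or treatments that could explain the event. An event with plausible timing and a second candidate cause is therefore an ordinary situation here, and it is the one the two definitions leave out.

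The call has consequences in four places:

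- **4.3.1:** the Grade 3 or higher criterion for interrupting or discontinuing study drug depends on relatedness.
- **4.3.2:** the Grade 4 or higher trigger for convening the iDMC depends on relatedness.
- **8.1.4:** non-fatal COVID-19 progression is recorded as an AE or SAE only if related to study drug or a study procedure. For expected ARDS events, association with study drug or procedures is one of the routes to recording.
- **8.5:** SUSAR reporting starts from a suspected adverse reaction, so the Investigator's call may influence it.

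**Working it through.** No sample size, power or error rate is involved, and the plan gives no figure to reproduce. The check crosses timing (two levels) with other cause (three levels) and classifies each cell under the three sections.

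| Time course | Other cause | 8.1.3 | 8.1.1 | 4.3 |
|---|---|---|---|---|
| rules out causality | none | neither | not a reaction | not related |
| rules out causality | identified, not clear | No | not a reaction | not related |
| rules out causality | clear | No | not a reaction | not related |
| consistent | none | Yes | reaction | possibly related |
| consistent | identified, not clear | **neither** | reaction | possibly related |
| consistent | clear | **neither** | reaction unless ruled out | not related |

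1. **Exhaustiveness.** With other cause taken simply as absent or present there are 2 × 2 = 4 combinations. One is Yes, one is No, and 4 − 2 = 2 are neither. Splitting other causes into clear and not clear gives 2 × 3 = 6 cells, of which 1 is Yes, 2 are No and 3 are neither.
2. **The harmless gap.** Timing that excludes causality with no other suspected cause (row 1) is unrelated under both 8.1.1 and 4.3. It shows that the No definition is incomplete but would not mislead anyone.
3. **The gap that matters.** Row 5 is related under 8.1.1 and 4.3, yet 8.1.3 withholds Yes. Both other sections disagree with 8.1.3 here.
4. **The partial case.** In row 6, 4.3 itself allows the event to be called unrelated, so it does not conflict with withholding Yes. Section 8.1.1 still counts the event as a reaction unless the clear cause is enough to rule the drug out, and 8.1.3 still does not permit No.
5. **Direction of error.** The only Yes cell (row 4) is related under 8.1.1 and 4.3. The reverse fails in row 5. The literal Yes is therefore strictly narrower, and any error from withholding it runs toward under-classification.
6. **Conflict inside 8.1.3.** A label that includes possibly related, and a sentence equating the definition with a reasonable possibility, do not fit a condition that any identifiable alternative defeats.
7. **Effect on 8.1.4.** A progression event already has an identifiable cause, the disease. Under the literal Yes wording, a non-fatal progression event could not be called related to study drug, so that exception could not be used.

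**The case against.** The strongest reply is that the literal definition will not govern practice. The disputed event fails No as well as Yes. The label, the reasonable-possibility sentence and the list of factors to weigh could all lead an Investigator to Yes. The default in 4.3 sits directly above 4.3.1 and 4.3.2 and arguably governs them more closely than 8.1.3 does. For 8.5, the expedited report is the task of the Sponsor or designee, and adverse reaction is defined broadly in 8.1.1.

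Several safeguards also bypass the causality call:

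- In 4.3.1, one of the three criteria depends on relatedness, and action is discretionary.
- In 4.3.2, the triggers for three or more safety discontinuations, and for three or more similar SAEs or Grade 3 AEs, do not depend on relatedness.
- In 8.1.4, fatal progression is recorded, and expected ARDS events are also recorded if unusually severe or frequent or if their severity changes.
- In 8.3, SAEs go to the safety group within 24 hours without a relatedness condition, subject to the progression exemption.
- Safety is summarised by treatment received (9.2.2), and the iDMC sees unblinded data (9.2.4), so a comparison with placebo does not rest on Investigator causality.

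All of this stands, and it limits the harm. It does not remove the gap. If some Investigators follow the looser sentence and others the explicit condition, the related-event counts will differ by site for reasons of wording. The three-patient triggers do not replace a Grade 4 trigger that has no such minimum, and they cannot count progression events that were never recorded.

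**Conclusion.** The definitions in 8.1.3 are not exhaustive. The no-other-cause condition conflicts with the rest of that section and with 8.1.1. Its conflict with 4.3 is limited to other causes that are identifiable but not clear. The consequence is a risk of inconsistent coding between sites and of under-classifying related events. It affects one criterion in 4.3.1, one trigger in 4.3.2, recording under 8.1.4 and potentially 8.5.

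The size cannot be computed, because the documents give no rate of AEs with competing causes. That such causes will often exist is an assumption drawn from the population and the background therapy.

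A reader might infer more: that 8.1.3 flatly contradicts 4.3, that Yes is close to unattainable, that under-classification is certain, or that every safety mechanism using relatedness is disabled. The documents do not support this. Section 4.3 exempts events with a clear other cause, 8.1.3 contains wording that points to Yes, and several triggers and recording routes work without a causality call.

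**What to change.** Delete the condition that no other cause can be identified, and bring 4.3, 8.1.1 and 8.1.3 to one standard with two categories that are exhaustive and do not overlap:

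- **Yes:** a causal relationship with study drug is at least a reasonable possibility, meaning it cannot be ruled out, even if other causes are also possible.
- **No:** every other event, meaning there is no reasonable possibility.

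State in 4.3 that a clear other cause supports No only when it leaves no reasonable possibility of a causal relationship with study drug. Without that sentence, an event with a clear alternative and a remaining reasonable possibility could meet both categories, and the gap would become an overlap.

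The cost is revised protocol and eCRF-guideline wording. Somewhat more events will be coded as related.

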8.1.4 Expected Acute Respiratory Distress Syndrome Events

As events of progression of the patient's underlying COVID-19 diagnosis will be captured as efficacy endpoints (see Section 7.1), these events should not be reported as AEs or SAEs unless considered related to the study drug or a study procedure or if the outcome is fatal during the study and within the safety reporting period. Additionally, expected events for ARDS that are perceived by the Investigator to occur with reasonable frequency in the day-to-day care of patients with ARDS treated in an ICU setting with mechanical ventilation will not be reported as AEs. Examples of events that are expected in the course of ARDS include transient hypoxemia, agitation, delirium, etc. Such events, which are often the focus of prevention efforts as part of standard ICU care, will not be considered reportable AEs unless the event is considered by the Investigator to be associated with the study drug or study procedures, is unexpectedly severe or frequent, or is a change of severity for an individual patient with ARDS.

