As events of progression of the patient's underlying COVID-19 diagnosis will be captured as efficacy endpoints, these events should not be reported as AEs or SAEs unless considered related to the study drug or a study procedure or if the outcome is fatal during the study and within the safety reporting period. Additionally, expected events for ARDS that are perceived by the Investigator to occur with reasonable frequency in the day-to-day care of patients with ARDS treated in an ICU setting with mechanical ventilation will not be reported as AEs. Examples of events that are expected in the course of ARDS include transient hypoxemia, agitation, delirium, etc. Such events, which are often the focus of prevention efforts as part of standard ICU care, will not be considered reportable AEs unless the event is considered by the Investigator to be associated with the study drug or study procedures, is unexpectedly severe or frequent, or is a change of severity for an individual patient with ARDS.

PHARMACOKINETIC ENDPOINT:

The PK endpoint is the plasma exposure of FP-025 at each dose level. Sampling times will be as follows:

- Day 1 (Visit 2): pre-dose, 1 hour (± 10 minutes), 3 hours (± 10 minutes), and 8 hours (± 10 minutes) post the first morning dose of study drug;

Note: If the patient is randomized in the afternoon on Day 1 (Visit 2), this will be performed after the morning dose of study drug on Day 2.

- Day 4, Day 7, Day 14, and Day 21: within 1 hour (± 10 minutes) prior to the morning dose; and
- Day 28: within 1 hour (± 10 minutes) prior to the morning dose and 1 hour (± 10 minutes) post-morning dose.

STATISTICAL ANALYSES:

The following analysis populations are defined for this study:

Intent-to-Treat (ITT) Population: The ITT Population is defined as all randomized patients. The ITT Population will be the primary population for analysis of efficacy data. Efficacy analyses will be based on the assigned treatment group.

Safety Population: The Safety Population is defined as all randomized patients who receive at least 1 dose of study drug. All safety data will be analyzed using the Safety Population. Safety analyses will be based on the treatment actually received.

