3 STUDY DESCRIPTION

3.1 Summary of Study Design

This is a Phase 2/3, randomized, double-blind, placebo-controlled, multicenter study to evaluate the efficacy and safety of FP-025 in adult patients with severe to critical COVID-19 with associated ARDS. The patients in each phase (Phase 2 and Phase 3) will be analyzed separately.

Each phase will consist of a Screening Visit, Treatment Period, and Follow-Up Period for a total study duration of approximately 60 days.

3.1.1 Phase 2

After eligibility is confirmed, approximately 99 patients will be randomized in a 1:1:1 ratio to receive FP-025 100 mg BID, FP-025 300 mg BID, or placebo BID for 28 days. During Phase 2, randomized patients will be stratified by the use of invasive mechanical ventilation at the time of randomization (yes or no). At least one-third of patients should be on invasive mechanical ventilation to ensure that treatment benefits can be assessed for patients at different severity levels.

Patients with Grade 3 to Grade 4 heart failure, Stage 3 or greater COPD, persistent asthma, and mild liver disease (ie, Child-Pugh Class A) will not be excluded from the study. The independent Data Monitoring Committee (iDMC) will independently monitor safety of the entire population and in different subgroups and may make recommendations as it deems appropriate. During Phase 2, no limitation in enrollment of subgroups is expected, unless clear safety signals arise in those subgroups during iDMC reviews.

The reason for hospital admission, the standard of care followed for each patient and center, and whether any care decisions were based on resource limitations will be clearly documented for all patients beginning on Day 1 (Visit 2). All patients will be allowed to receive standard of care and/or emergency use authorization (EUA) medications and treatment for COVID-19; however, the study drug should be discontinued for other non-standard of care concomitant medications used with the intent of directly treating COVID-19 unless there is prior Medical Monitor or Sponsor approval for the patient to remain on the study drug. If the use of concomitant medications necessitates study drug discontinuation, the patient should be encouraged to remain in the study and to follow-up for key study visits (Day 28 and Day 60) but will not be required to attend every study visit. If the patient withdraws, he/she should complete the Early Termination Visit.

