4.3.2 Criteria for Potential Study Termination

In the event that any of the following is encountered, the iDMC will convene to determine if the study must stop enrollment and/or to recommend modification to the protocol (ie, decrease or change the dose of study drug, modify dosing schedule, or terminate the study, as described in the iDMC Charter):

- \geq Grade 4 (CTCAE version 5.0) reaction considered related to study drug;
- \geq 3 patients are discontinued from treatment for safety reasons; or
- \geq 3 patients experience similar SAEs or Grade 3 (CTCAE version 5.0) AEs regardless of relatedness to study drug.

Note: All \geq Grade 3 (CTCAE) laboratory abnormalities should be confirmed with a repeat test within 24 hours to confirm the abnormality.

The following will not be considered as criteria for study termination:

- Grade 3 nausea if resolves to \leq Grade 1 within 72 hours;
- Grade 3 fatigue, malaise, or insomnia if resolves to \leq Grade 1 within 72 hours; and
- \leq Grade 4 isolated electrolyte abnormalities that resolve with or without intervention to \leq Grade 1 within 72 hours.

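### The expected-ARDS-event exemption is not limited to patients ventilated in an ICU at onset and leaves serious events unresolved, so the exempted event types cannot be completely compared between arms

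*Combined protocol and SAP*

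**What the plan says.** Section 8.1.4 contains two separate rules, both repeated in the synopsis under Safety Endpoints.

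The first covers progression of COVID-19: "these events should not be reported as AEs or SAEs unless considered related to the study drug or a study procedure", or unless the outcome is fatal. That rule is not at issue here.

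The second covers expected ARDS events. Those the investigator perceives as reasonably frequent in the care of "patients with ARDS treated in an ICU setting with mechanical ventilation will not be reported as AEs". The list is illustrative and open: "Examples of events that are expected in the course of ARDS include transient hypoxemia, agitation, delirium, etc". An event returns to AE reporting in three situations:

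- "unless the event is considered by the Investigator to be associated with the study drug or study procedures" (relatedness);
- it "is unexpectedly severe or frequent, or is a change of severity for an individual patient with ARDS" (two further routes: unexpected severity or frequency, and individual change).

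Seriousness is not among the exceptions.

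Elsewhere, Section 8.1 has all AEs recorded from first dose to Day 60, and Section 8.3 requires all SAEs over the same period to be reported within 24 hours. Section 4.3.2 convenes the iDMC when three or more "patients experience similar SAEs or Grade 3 (CTCAE version 5.0) AEs regardless of relatedness to study drug".

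**The concern.** Safety and tolerability are a primary objective (Section 2.1). When an event is common in the background, an investigator looking at one patient can seldom tell whether the drug contributed. The evidence lies in the rate by arm. A rule that keeps such events off the AE form, except where someone already suspects the drug or finds the event unusual, leaves that rate incomplete.

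The rationale for the exemption is routine ICU care of ventilated patients. If the wording reaches patients who are not in that setting, safety data are lost where the rationale does not apply. If it also leaves sites unsure about serious events, a 24-hour reporting duty depends on which section a site reads.

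**Working it through.** The plan states no figure on this point, so the check is mainly one of text.

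**1. Who is covered.** In Section 8.1.4 the ICU-and-ventilation phrase describes the patients among whom the event is common. No sentence says that the trial patient must be in that state at onset, or that the exemption ends at extubation or discharge. Three facts then matter:

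- Section 4.1 admits patients on high-flow nasal cannula, on non-invasive positive pressure ventilation, or with respiratory failure where these therapies cannot be given.
- For Phase 2, Section 3.1.1 says: "At least one-third of patients should be on invasive mechanical ventilation". With about 99 patients, the floor is 99 × 1/3 = 33 on invasive ventilation, so up to 99 − 33 = 66 may be off it at entry. This is a ceiling derived from a floor. It describes entry only and says nothing about ICU location or later intubation. Some of the 66 may be on non-invasive ventilation, and Section 8.1.4 does not say whether that counts as mechanical ventilation.
- Discharged patients keep dosing at home to Day 28 (Section 3.1.1), and AE collection runs to Day 60 (Section 8.1), which is 60 − 28 = 32 days after the end of treatment.

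**2. Whether the exceptions bring these events back.** Take new delirium of usual severity in a patient on high-flow oxygen or at home.

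- *Relatedness.* Two rules apply, and they differ. Section 4.3 treats an AE as possibly related unless it is clearly unrelated or has another clear cause. Section 8.1.3 allows a Yes only if no other cause can be identified. In this illness another cause will often be identifiable, so under Section 8.1.3 this exception would seldom apply.
- *Unexpected frequency.* This is an aggregate judgement. A blinded investigator (Section 5.3) with few patients, and with the events themselves unrecorded, is poorly placed to make it.
- *Change of severity.* New onset could count as a change from none. Section 8.1 uses similar language for conditions already present at baseline, where it means worsening. Section 8.1.4 does not say which sense applies.

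The result is ambiguous. On one plausible reading the event is not recorded.

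**3. Serious events.** The texts side by side:

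- Section 8.1.4, progression rule: names both AEs and SAEs, with a fatal-outcome exception.
- Section 8.1.4, expected-event rule: names AEs only, with no seriousness exception.
- Section 8.2: defines an SAE as an AE or adverse reaction meeting a criterion, and refers to the Section 8.1.4 examples inside its paragraph on what not to report as an SAE.
- Sections 8.1 and 8.3: all AEs recorded, all SAEs reported.

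A site could conclude that delirium prolonging hospitalization is exempt (Sections 8.1.4 and 8.2) or that it is due within 24 hours (Section 8.3). The documents do not settle it.

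**4. Other capture.** Tables 2 and 3 of Appendix A schedule no assessment of delirium or agitation. The nearest item is the physical examination, whose telemedicine form may note orientation; it is not an event record. Oxygen saturation is collected at visits, so hypoxemia is partly visible.

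**5. The Section 4.3.2 count.** It is meant to ignore relatedness. An exempt Grade 3 event enters it only through the exceptions above, one of which is a relatedness judgement.

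**The case against.** The other side has real strength.

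A reader might infer that serious ICU complications are simply not reportable. The documents do not say that. The expected-event sentence is confined to AEs, Section 8.3 calls for all SAEs, and unexpectedly severe or drug-associated events are reportable in any case. What stands is an unresolved conflict between sections.

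A reader might also infer that the arms cannot be compared on safety. That is too strong. Blinded investigators apply one rule in every arm. Deaths, ventilation status, the ordinal scale, laboratory tests, vital signs and ECGs are still collected. Only the exempted event types are compared incompletely.

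It can be said that the section speaks of events expected in the course of ARDS and of standard ICU care, so applying it to a patient at home is a literal reading and not the natural one. The individual-change exception may also restore new-onset events. Both points are fair. They show that the text is unclear, which is a reason to clarify it.

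Finally, keeping routine ICU events out of a count of three similar Grade 3 AEs is a defensible choice, since background rates alone could trip it. The other Section 4.3.2 triggers (related reactions of Grade 4 or higher, and three safety discontinuations) remain. That reasoning supports an exemption for ventilated ICU patients. It does not support one whose reach is unstated.

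**Conclusion.** The point holds as a gap in scope and an unreconciled conflict. Section 8.1.4 and the synopsis do not tie the exemption to the patient's own setting at onset, and they do not say that events meeting a Section 8.2 criterion stay reportable. As a result, rates of transient hypoxemia, agitation, delirium and similar events cannot be completely compared between arms, and some may be missing from the Section 4.3.2 count.

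The only size the documents support is the Phase 2 ceiling of about 66 of 99 patients not on invasive ventilation at entry, plus those later extubated or discharged. No loss of power can be put on it: the documents give no delirium rate and no fraction of exempt events that would be recorded, and Section 9.2.2 plans summaries of safety data, not tests.

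The conclusion rests on sites following the text as written, without a completion guideline or training note that narrows it. It is a cheap improvement to make; it does not invalidate the design.

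**What to change.** Amend Sections 8.1.4 and 8.2 and the synopsis as follows:

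1. Limit the exemption to patients receiving mechanical ventilation in an ICU at event onset, and say whether non-invasive ventilation counts.
2. Reconcile Sections 8.1.4 and 8.2 with Sections 8.1 and 8.3 by stating that events meeting a Section 8.2 seriousness criterion are reported as SAEs. The separate COVID-19 progression rule stays as it is.
3. Record the named exempt events (transient hypoxemia, agitation, delirium) on a short eCRF checklist, for example occurrence, onset date and highest CTCAE grade, tabulated by arm for the iDMC.

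The cost is protocol wording, one eCRF form, more AE entry for non-ventilated and discharged patients, and some additional 24-hour SAE reports, including in ventilated patients. No visit or procedure is added. Closing the list of exempt events is not proposed, because it would turn every other routine ICU event into an AE. The price is that unnamed expected events in ventilated ICU patients, when not serious, stay uncounted.
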